#### Sample size and power:

The study was powered to measure significant improvements in renal function. To estimate the required sample size we assumed that the estimated glomerular filtration rate (eGFR) would improve from 34 mL/min/1.73 m^2 to 43 mL/min/1.73 m^2 as reported in a recent study by Fairbanks et al [29]. This is a conservative estimate since the renal sparing effects of everolimus are larger than those of sirolimus. A sample size of 12 in each group will have 80% power to detect a difference in means of -9.0 (the difference between a Group 1 mean of 34.0 and a Group 2 mean of 43.0) assuming that the common standard deviation is 7.5 using a two group t-test with a 0.050 two-sided significance level. Fairbanks did not report standard deviations for eGFR, however, a simulation study suggests that the standard deviation at baseline was 7.5, and the standard deviation following conversion was 16. We therefore, considered the sample size requirement for a range of standard deviations, shown in the Figure below. If the common standard deviation was 16, then 51 patients per group would be required to detect a significant difference of 9.0 with 80% power. This sample size may not be feasible for a pilot study such as this. However, 12 per group is feasible and can be justified by the lower limit of standard deviation reported in Fairbanks.

IRB # 38115 Version: December 28, 2018

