# 4.0 Inclusion and Exclusion Criteria

Study Population: This will be a pilot study which will include 12 adult deceased donor liver transplant recipients in each study arm.

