# **10.0 Study Withdrawal/Discontinuation:**

This is a small pilot study (12 randomized patients in each of two groups) and in view of the small patient cohort. Stopping rules for this study will therefore be based on patient safety.

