#### · Graft Loss/Re-transplant

#### Premature Patient withdrawal:

Patients may voluntarily withdraw from the study or be dropped from it at the discretion of the investigator at any time. Patients will be withdrawn from the study if any of the following occur:

- Withdrawal of consent
- Lost-to follow-up
- Graft loss/re-transplant
- Death
- Serious life threatening adverse event.

If such withdrawal occurs, or if the patient fails to return for visits, the primary reason for a patient's premature withdrawal from the study will be recorded.

For patients who are lost to follow-up, "due diligence" will be shown by documenting in the patient record steps taken to contact the patient, e.g. dates of telephone calls, registered letters, etc.

Patients who are prematurely withdrawn from study medication or from the study after randomization will not be replaced. Patients who withdraw or screen fail prior to randomization will be replaced.

Patients who prematurely discontinue everolimus will be followed for any SAE occurring within 30 days following the last dose of everolimus. These SAEs will be reported on the SAE form.

Patients who become pregnant while taking everolimus or are taking a prohibited immunosuppressive medication not allowed by the protocol will be discontinued from the investigational drug and from the study.

If the everolimus trough level ≥ 3 ng/mL cannot be maintained, patients will be discontinued from the study.

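### The stated 80% power is correct for 12 analysed values per arm, but 12 is the number randomized and no loss is allowed for, so power is about 67–76% with 9 to 11 evaluable per arm

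*Combined protocol and SAP*

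**What the plan says.** The sample size paragraph of section 11.0 states that "A sample size of 12 in each group will have 80% power to detect a difference in means of -9.0". The difference is "the difference between a Group 1 mean of 34.0 and a Group 2 mean of 43.0", "assuming that the common standard deviation is 7.5" and "using a two group t-test with a 0.050 two-sided significance level". The same paragraph discloses a less favourable case: "If the common standard deviation was 16, then 51 patients per group would be required to detect a significant difference of 9.0 with 80% power". It accepts 12 per group on grounds of feasibility and the lower SD.

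Other sections fix what the 12 counts. Section 4.0 says: "This will be a pilot study which will include 12 adult deceased donor liver transplant recipients in each study arm". Section 10.0 says: "This is a small pilot study (12 randomized patients in each of two groups". Under premature withdrawal, section 10.0 adds: "Patients who are prematurely withdrawn from study medication or from the study after randomization will not be replaced". Only patients lost before randomization are replaced.

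Several rules take a patient out of the study, not only off the drug:

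- Section 10.0 lists withdrawal of consent, loss to follow-up, graft loss or re-transplant, death and serious life-threatening adverse events. It also gives a list of serious toxicities, and a rule on everolimus trough levels that cannot be maintained.
- Section 7.0 adds a rule on prolonged or repeated everolimus interruption.

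Section 11.0 contains no allowance for loss, no missing-data method and no named visit for the primary endpoint.

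**The concern.** Power depends on the number of values analysed, not on the number randomized. The power statement says 12 in each group without saying which is meant. If 12 analysed values only just reach 80%, and 12 is also the most that can be available, any missing value puts the trial below its stated power. With 24 patients, each loss is a visible fraction of the information.

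What is at stake is how the result is read. Section 3.0 describes a pilot that is to assess superiority, and section 11.0 says that the study was powered for improvement in renal function. A reader of a null result would set it against 80% when the analysed data may have offered noticeably less. The paragraph tells that reader about the SD, but not about the full-data condition.

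**Working it through.** **Inputs, all from the sample size paragraph of section 11.0:** difference 9.0 (43.0 − 34.0), common SD 7.5, two-group t-test, two-sided α = 0.05. From sections 4.0 and 10.0: 12 randomized per arm, 24 in total, no replacement after randomization.

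**Formula.** For n₁ and n₂ analysed values, df = n₁ + n₂ − 2 and the noncentrality parameter is δ = 9 / (7.5 × √(1/n₁ + 1/n₂)). Power is the probability that a noncentral t variable with these parameters falls outside ± the 97.5% point of the central t distribution.

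**Reproducing the plan's figures**

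- 12 and 12 at SD 7.5: δ = 1.2 / √(1/6) = 2.939, df = 22, critical value 2.074, power **80.2%**. The stated 80% is confirmed.
- 51 per group at SD 16: δ = 9 / (16 × √(2/51)) = 2.840, power 80.3%. With 50 per group it is 79.5%, so the stated 51 is confirmed.

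A normal approximation would give 83.6% at 12 per arm, and 50 rather than 51 per group at SD 16. It does not match the plan, so the t-test is the right basis.

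**Power by number of evaluable patients, SD 7.5**

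| Evaluable (one arm / other arm) | δ | df | Power |
|---|---|---|---|
| 12 / 12 | 2.939 | 22 | 80.2% |
| 12 / 11 | 2.875 | 21 | 78.3% |
| 11 / 11 | 2.814 | 20 | 76.3% |
| 12 / 10 | 2.803 | 20 | 76.0% |
| 10 / 10 | 2.683 | 18 | 71.8% |
| 9 / 9 | 2.546 | 16 | 66.7% |

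Since 11 per arm gives 76.3%, 12 is the smallest equal group size that reaches 80%. There is no margin. One missing value costs 80.2 − 78.3 = 1.9 points. Three missing in each arm cost 80.2 − 66.7 = 13.5 points.

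**Illustration with assumed loss rates.** The documents give none. Weighting the power over binomial numbers evaluable, the average is 77.8% at 5% loss per patient, 75.1% at 10% and 69.0% at 20%, with the same rate in both arms. With independent losses, the chance that all 24 values are available is 0.95²⁴ = 29% at 5% loss and 0.90²⁴ = 8% at 10%.

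**Comparison with the SD.** At SD 16 with all 24 values, δ = 9 / (16 × √(1/6)) = 1.378 and power is 26.1%. One missing value then takes it to 25.1%, and 9 per arm to 20.2%.

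**The case against.** The strongest reply is that nothing has been miscalculated and the effect is small. Both stated sample sizes reproduce, and not replacing randomized patients is ordinary practice. One missing value costs the same as raising the SD from 7.5 to about 7.7. Losing three patients in each arm is equivalent to an SD of about 8.8, well within the plan's own range of 7.5 to 16. The section also admits that its SD is the favourable one and that this is a pilot limited by feasibility. All of this stands, and it is why the point is minor. It does not remove the point, because the SD is disclosed as a condition of the 80% and complete data are not.

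Some stronger readings are tempting, but the documents do not support them:

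- *All 24 patients must complete some 20 months of follow-up.* Section 11.0 names no analysis visit. Randomization is at 90 to 120 days and visits fall at months 6, 12 and 24 after transplant. If the endpoint were read at month 6, exposure to loss would be about 2 to 3 months. What is needed is 24 usable values at the analysis visit, not 24 completers. Section 10.0 also separates withdrawal from study medication from withdrawal from the study, so a withdrawal need not mean a missing value. However, the only follow-up it describes after everolimus is stopped early is for serious adverse events over 30 days.
- *Power will be about 75% or 69%.* Those averages rest on assumed loss rates. Only the table by number evaluable follows from the plan.
- *The point is independent of the SD.* The missing allowance is, but every figure in the table is conditional on SD 7.5.
- *The data safety monitoring board was given an inflated figure.* The documents say that it receives progress reports. They do not show that the power figure was among them.

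**Conclusion.** The concern holds as a matter of incomplete disclosure, and it is minor. The 80% is correctly computed for 12 analysed values per arm. The design delivers it only with no missing primary values, because 12 is also the number randomized, losses after randomization are not made up and no allowance is stated. At the plan's own inputs, power falls to 76.3%, 71.8% and 66.7% with 11, 10 and 9 evaluable per arm.

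This rests on the plan's difference of 9.0, its SD of 7.5, the unadjusted two-sided t-test and analysis of observed values only. How many values will be missing cannot be determined from the documents. The interruption and trough-level rules can apply only to Arm A, so losses may be unequal. The SD remains the larger threat to power.

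**What to change.** Keep 24 patients. In the sample size paragraph of section 11.0, replace the power sentence with wording such as: *Twelve evaluable patients per arm give 80% power to detect a difference of 9.0 at a common SD of 7.5 (two-group t-test, two-sided 0.05). With 9 to 11 evaluable of the 12 randomized per arm, power is about 67–76% at that SD, and lower at larger SDs.* Define evaluable there as having a usable primary creatinine clearance value at the analysis visit.

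In section 4.0, describe the 12 per arm as randomized, to match section 10.0, which already does.

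The cost is two or three sentences. No patients are added, and no treatment rule or analysis changes. The stated power simply reads less favourably.

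### The 80% power applies a baseline SD of 7.5 to both arms; at the plan's own post-conversion SD of 16, 12 per arm gives 26% to 39%

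*Combined protocol and SAP*

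**What the plan says.** The sample size paragraph in Section 11.0 opens with "The study was powered to measure significant improvements in renal function". It takes two eGFR means from a study of conversion to sirolimus, 34 before and 43 after. It makes them the two groups of a t-test ("the difference between a Group 1 mean of 34.0 and a Group 2 mean of 43.0") and obtains 80% power with 12 per group, "assuming that the common standard deviation is 7.5 using a two group t-test with a 0.050 two-sided significance level".

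On where the SD comes from, it says that the cited study "did not report standard deviations for eGFR", but that a simulation suggests "the standard deviation at baseline was 7.5, and the standard deviation following conversion was 16". It adds that if the common SD were 16, "then 51 patients per group would be required", and comments: "This sample size may not be feasible for a pilot study such as this". It ends by saying that "12 per group is feasible and can be justified by the lower limit of standard deviation reported in" that same study.

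Earlier in Section 11.0 the primary endpoint is 24-hour creatinine clearance, compared between arms by t-test, with regression only if the groups are found to differ on characteristics such as demographics or disease. Section 3.0 describes a pilot with a superiority aim.

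**The concern.** A before-and-after contrast has been recast as a between-arm contrast, and only the smaller of the two SDs has been carried over. The between-arm test uses values measured after randomization. Arm A is by design the converted group, and the plan's own SD for converted patients is 16, more than twice the 7.5 used. The two SDs are not the low and high ends of uncertainty about one quantity. The plan assigns them to two different times, so calling 7.5 a lower limit does not justify its use at follow-up.

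The justification is also inconsistent in itself: it relies on an SD described as reported in a study that the same paragraph says reported none.

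What is at stake is how a null result is read. With a superiority aim and a 0.05 threshold, a non-significant result set against a stated 80% power looks like evidence against renal sparing. If the real power is 26% to 39%, it is close to uninformative.

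**Working it through.** **Inputs from Section 11.0:** difference 9.0; 12 per arm; two-sided 0.05; SD 7.5 at baseline and 16 after conversion; two-group t-test. **Assumption:** Arm B's follow-up SD is not given, so it is varied from 7.5 to 16.

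**Method.** Noncentral t with 22 degrees of freedom and critical value 2.074.
- Combined SD: σ = √[(SD_A² + SD_B²)/2]
- Standard error: SE = σ√(2/12) = 0.408σ
- Noncentrality: δ = 9/SE
- Expected 95% CI half-width: about 2.074 × SE

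**Step 1: the plan's figures.** With 7.5 in both arms, SE = 3.06, δ = 2.94 and power is 80.2%; 12 is the smallest number per arm that reaches 80%. With 16 in both arms, the smallest number is 51 (80.3%). Both of the plan's figures reproduce.

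**Step 2: each mean with the SD the plan gives it** (34 with 7.5, 43 with 16). σ = √[(256 + 56.25)/2] = 12.49, SE = 5.10, δ = 1.76, power 39.3%. A simulation of 200,000 trials gives 39.9% for the pooled t-test and 38.1% for Welch's test.

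**Step 3: SD 16 in both arms.** SE = 6.53, δ = 1.38, power 26.1%.

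| SD Arm A / Arm B | Power, 12 per arm | Chance of missing a true 9 | n per arm for 80% | 95% CI half-width |
|---|---|---|---|---|
| 7.5 / 7.5 | 80.2% | 20% | 12 | 6.3 |
| 16 / 7.5 | 39.3% | 61% | 32 | 10.6 |
| 16 / 16 | 26.1% | 74% | 51 | 13.5 |

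With Arm A at 16 and Arm B at 10, 12 or 14 (assumed), power is 35%, 32% or 29%.

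**Step 4: could baseline data restore the 80%?** Take a change score with baseline SD 7.5 in both arms, Arm A follow-up SD 16, and the same correlation r in both arms (assumed). The variance of change in an arm with follow-up SD s is 7.5² + s² − 2r(7.5)s. Reaching 80% needs r = 0.88, 0.90, 0.91 or 0.95 when Arm B's follow-up SD is 7.5, 9, 10 or 12. With Arm B at 14 or 16 it is not reached at any correlation (maximum 79.5% and 70%). Regression on baseline does better than a change score when Arm B's SD is large, but in simulation it still needs a correlation of roughly 0.85 to 0.89. The plan states no correlation, and neither analysis is its primary test.

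**Step 5: does 7.5 fit this population?** Section 4.0 requires eGFR of at least 30. A normal distribution with mean 34 and SD 7.5 puts P(Z < (30 − 34)/7.5) = 30% below that floor. So the borrowed mean and SD together do not describe the patients who can enter. This does not show that 16 is right, only that 7.5 has not been shown to apply.

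**The case against.** The strongest reply is that the plan hides nothing. The 80% is stated as conditional on SD 7.5. Both SDs are given and labelled, and a reader told that SD 16 needs 51 per group can see that 12 falls well short. The trial calls itself a pilot, and 12 was what could be recruited. A figure covering a range of SDs is missing from the text available here. All of this stands. But feasibility justifies the number 12, not the SD of 7.5. The sentence introducing the figure speaks of sample size requirements, and the visible text never gives the power of the chosen 12 at SD 16.

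A second reply is that 26% to 39% is no better founded than 80%: both SDs are simulated eGFR values from another study, the endpoint is 24-hour creatinine clearance, and Arm B's SD is unknown. That also stands. It argues for presenting every figure as conditional, the 80% included.

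Third, the plan calls the difference of 9 conservative because it expects everolimus to do better than sirolimus. A larger effect would raise power, but 80% with 12 per arm would need a true difference of about 15.0 (SDs 16 and 7.5) or 19.1 (16 in both). The plan gives no figure of that size.

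**Conclusion.** The concern holds. The arithmetic of the 80% is right; the SD put into it is, by the plan's own label, a baseline SD applied to a follow-up comparison. At the plan's post-conversion SD, power for a difference of 9 is 39% if only Arm A has SD 16 and Arm B stays at 7.5, and 26% if both arms have 16. The expected confidence interval half-width (10.6 to 13.5) then exceeds the effect sought.

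These figures rest on a true difference of 9, the unadjusted t-test, no losses, no multiplicity correction, and the simulated eGFR SDs carrying over to creatinine clearance. Unreplaced withdrawals (Section 10.0) or a Bonferroni correction (Section 11.0) would lower them. This should be fixed, but it does not invalidate the trial: it changes what the trial may claim, not how it is run.

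**What to change.** Replace the lower-limit justification and the opening claim of being powered with a conditional statement in Section 11.0, along these lines:

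> With 12 patients per arm, power to detect a difference of 9 is 80% only if the follow-up SD is 7.5 in both arms. At the estimated post-conversion SD of 16 it is 39% (Arm A only, Arm B at 7.5) to 26% (both arms). The number 12 was chosen for feasibility. The value 7.5 is a simulated baseline SD. Both SDs are for eGFR, not 24-hour creatinine clearance, so these figures are conditional.

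Keep the t-test. Report the between-arm difference with its 95% confidence interval, and interpret a non-significant result from that interval rather than against 80% power.

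The cost is a change of wording and one interval in the report, with no extra patients, visits or tests. The downside is a less favourable stated power.

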# 12.0 Privacy and Confidentiality Considerations

All data forms and study specific information will be kept in locked file cabinets and in a password protected computer database with access limited to the PI, clinical research nurses, and sponsor designees. Any presentation or publication of the data will be done in aggregate fashion without identifiers.

A Data Safety Monitoring Board (DSMB) will review the study progress reports provided to the DSMB by the study team and statistician. A DSMB report will be generated by the DSMB and forwarded to the IRB and the PI. A copy of any interim DSMB reports will be included with continuing review reports submitted by the PI for IRB review.

# **13.0** Data and Safety Monitoring Plan:

This study is a prospective randomized open label pilot study examining the impact of conversion to everolimus therapy from standard calcineurin inhibitor immunosuppression. Oversight for the conduct of the study will be provided by the PI, [name] MD, and the clinical research nurse. They will ensure that all eligibility and consent requirements are met prior to a subject's participation on study and that all study procedures and adverse event reporting occur according to the IRB approved protocol. They will follow all study participants, while on study treatment, on a real-time basis for development of adverse events and study end points, utilizing scheduled and as needed physical examinations and laboratory studies. They will make certain that all adverse events are recorded and reported according to the Penn State HSPO (Human Subjects Protection Office) guidelines and that the IRB is notified in a timely manner of any significant safety or data concerns which arise from study review.

Primary monitoring of the study will be performed by the study team, who will review accrual, adverse events, and dose limiting toxicities on a real-time basis. Cumulative adverse events and study toxicities will be reviewed weekly. The study team will make decisions regarding dose escalation, and cessation of accrual.

A Data Safety Monitoring Board (DSMB) will review the study progress reports at six month intervals, with study progress reports provided to the DSMB by the study team and statistician. A DSMB report will be generated by the DSMB and forwarded to the IRB and the PI. A copy of any interim DSMB reports will be included with continuing review reports submitted by the PI for IRB review.

IRB # 38115 Version: December 28, 2018

# 14.0 Compensation

For patients randomized into Group A who are receiving Everolimus medication will be reimbursed for travel expenses in order to return twice per week during the first 3 months after randomization to have the Everolimus blood level checked at Hershey Medical Center's Laboratory. The reimbursement for travel expense is 24 cents per mile based on the 2013 Internal Revenue Service standard mileage reimbursement rate for medical travel and the total repayment will not exceed \$300.00. If the patient does not complete the study for any reason during the first 3 months after randomization, the patient will be paid for the medical travel expense up to the time of study discontinuation.

For patients randomized into Group B who are receiving Tacrolimus or Cyclosporin and Mycophenolic acid medications will not receive any payment or compensation for being in this research study because they may continue to have medication blood levels checked at the local laboratory with blood level results faxed to [name] office

# 15.0 Drugs, Biologics, or Devices

Everolimus (Zortress) IND# 113882 0.25mg-0078-0417-20 0.5mg-0078-0414-20 0.75mg-0078-0415-20

Investigational Drug Service Pharmacy stores & dispenses investigational item

# 16.0 Records and Study Monitoring-

Primary monitoring of the study will be performed by the study team, who will review accrual, adverse events, and dose limiting toxicities on a real-time basis. Cumulative adverse events and study toxicities will be reviewed weekly. The study team will make decisions regarding dose escalation, cessation of accrual, and whether stopping rules have been reached. If stopping rules have been reached, this will be communicated to the IRB immediately

# 17.0 Facilities

Penn State Hershey Medical Center: at the UPC Surgery Clinic facilities & hospital inpatient area if patient is hospitalized.

